5 COMPENSATION

Participants will be compensated a total of \$90 in this research study. Specifically, they will receive \$30 in cash following Visit 1 and \$60 in cash following Visit 3. Participants who prefer to attend study visits at the Coro Building will also be given a parking voucher.

6 PRIMARY ENDPOINTS

Primary Endpoints:

- 1) Recruitment feasibility will be determined through examination of the percentage of eligible patients who enroll in the study.
- 2) Study feasibility will be calculated as the percentage of individuals who were enrolled and completed both the baseline assessment, intervention (when applicable), monitoring period, and end-of-treatment assessment. Feasibility of procedures will be defined as achieving a retention rate of 80%.
- 3) Patient acceptance of the intervention will be determined by mean satisfaction ratings rated on self-report measures with Likert-type questions and assessed through open-ended responding. Adequate acceptability will be defined as $\geq 80\%$ endorsement of being at least somewhat satisfied with participation.

STATISTICAL ANALYSIS PLAN

Values-Affirmation + Education Intervention Targeting Medication Adherence in Older Adults With Heart Failure

NCT05575375

8/1/2022

STATISTICAL DESIGN AND POWER

General Approach: Means and standard deviations will be used to describe continuous variables. Frequencies and percentages will be used to describe categorical data. For secondary, baseline descriptive, and exploratory analyses (see below), a p value $< .05$ will indicate statistical significance with a two-tailed test. Assumptions of relevant statistical tests such as assumptions of normality of the data distribution will be checked to ensure sound application and interpretation of inferential tests.

Intent-to-treat analyses will be used (i.e., all randomized participants will be included in analyses).

Analysis of Primary Endpoints: We will examine descriptive statistics (i.e., means, standard deviations, frequencies, percentages) to assess the primary endpoints. Means and standard deviations will be used to describe continuous variables. Frequencies and percentages will be used to describe categorical data.

- 1) Recruitment feasibility will be determined through examination of the percentage of eligible patients who enroll in the study.
- 2) Retention will be calculated as the percentage of individuals who were enrolled and completed both the baseline assessment, monitoring periods, and end-of-treatment assessment. Feasibility of procedures will be defined as achieving a retention rate of 80%.
- 3) Patient acceptance of the intervention will be determined by mean satisfaction ratings rated on self-report measures with Likert-type questions and assessed through open-ended responding. Adequate acceptability will be defined as $\geq 80\%$ endorsement of being at least somewhat satisfied with participation.

Analysis of Secondary Endpoints:

- 1) Self-reported medication adherence. Analysis of covariance (ANCOVA) will be used to examine differences in self-reported adherence between groups at end-of-treatment.
- 2) Electronically-monitored medication adherence measured the number of days $\geq 80\%$ of prescribed doses were taken. ANCOVA will be performed to examine differences in each outcome between groups at end-of-treatment.
- 3) Additional secondary analyses will use ANCOVA to examine differences in health-related quality of life, self-efficacy, perceived stress, affect and medication-related attitudes between groups at end-of-treatment.

All analyses of secondary endpoints will be performed with and without adjustment for covariates and baseline scores on the endpoint of interest to control for potential confounders.

Baseline Descriptive Analyses:

Descriptive statistics including means, standard deviations, frequencies, and percentages, will be calculated to characterize demographic, medical, and baseline psychosocial variables. Non-completers and completers will be compared using independent t-tests and chi-squared tests to assess for any differences in baseline characteristics. T-tests and chi-squared tests will also be used to assess differences in demographics and baseline medical and psychosocial characteristics between groups.

There will be no planned interim analysis in this small pilot study.

Exploratory analyses will also examine potential mechanisms of action that warrant examination in a subsequent fully-powered efficacy trial through testing of potential mediators (e.g., changes in self-efficacy, perceived stress, affect, or medication related-attitudes).

To assess potential mediators, multivariate regression analyses will be performed. The direct effects of the treatment condition on the mediator of interest (e.g., self-efficacy, perceived stress, affect, or medication-related attitudes), will be calculated using univariate linear regression. Next, the association between the mediator of interest on medication adherence will be calculated using a linear regression model that includes treatment condition and the mediator of interest as predictors of adherence (dependent variable). Coefficients from

these models will be used to test the indirect effect by the delta method (Sobel test). Mediation analyses will be performed with and without adjustment for covariates and baseline adherence to control for potential confounders.

Potential moderators (e.g., depressive symptoms, social support) will also be tested on an exploratory basis to assist in identifying potential moderators that warrant future study. To assess potential moderators, an interaction term will be created between the variable of interest and the study condition (intervention versus control group assignment) and entered as a predictor in a multivariate regression analysis.

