1 STUDY DESIGN

This research will examine the initial feasibility and acceptability of a values-affirmation, education, and skills-training intervention targeting heart failure (HF) medication adherence using the NIH Stage Model for Behavioral Intervention Development (Onken et al., 2014).

Design: This study is a Stage 1B trial and will use a randomized controlled trial design. Participants will be randomized 1:1 basis to the Values-affirmation Intervention condition (n = 25) or Usual Care (n = 25).

Setting: Study assessments and intervention delivery will occur either at the participant's home or The Miriam Hospital's Center for Behavioral and Preventive Medicine (CBPM). The location will be determined by participant preference. Data management and analysis will be housed at CBPM.

Study Duration: Study duration is estimated to be 21-24 months from the time of enrollment of the first subject to completion of data collection. Individual participants will complete the protocol within 8-10 weeks from the time of the baseline visit until the end-of-treatment assessment. Study completion is defined as completion of the baseline and end-of-treatment assessments, intervention content, and medication monitoring period.

Sample: 50 older adults with HF, ages 50 and older, who are enrolled in a CR program in Providence, Rhode Island will be recruited. We aim to recruit a sample that is 51% women and 30% individuals who identify as a NIH-defined racial or ethnic minority.

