Participants will also be asked to use a MEMS cap pill bottle to monitor medications for approximately 8 weeks (from the baseline assessment through the end-of-treatment assessment). We will monitor ONE medication per patient using the criteria adopted by Wu et al. Briefly, if the patient takes any HF medication *twice* a day, this medication will be MEMS-monitored. If all HF medications have the same daily prescription schedule, the β -blocker will be monitored. If the patient does not receive a β -blocker, the ACE inhibitor or the angiotensin receptor blocker will be used instead. If none of these drugs is prescribed, the aldosterone antagonist or statin, or digoxin or diuretic will be monitored. Participants will receive a MEMS bottle at the baseline visit and will be instructed to open it only when they actually take their medication; they will also be trained to keep track of unscheduled lid openings (i.e. refills, accidental openings) in a diary; these events will be removed prior to analysis. After the baseline visit, participants will enter a 30-day run-in for the assessment of baseline adherence. Participants will start using the cap on the day following the baseline visit (=time 0), and the intervention will start 30 days later; this 30-day period will be considered our baseline.

MEMS Caps are designed to be easily opened and closed, and to be very similar in design to pill bottles commonly used commercially. Participants will be asked to review their medication regimen with PI/SRA. Participants will be asked to fill the bottle with their prescribed heart medication selected for monitoring. Prior to use, a study team member will demonstrate appropriate use of the pill bottle and will invite participants to practice opening and closing the containers.

Written instructions will be provided to all participants, including study staff contact information. Participants will be encouraged to contact staff in the event of any questions or concerns. One week following the baseline assessment and initiation of monitoring, study staff will call the participant to ask if there are any questions regarding use of the devices. Any emergent questions will be answered.

4.1.2 Intervention Session + Pill Count Check OR Pill Count Check only (Visit 2)

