4.1.3 Final Evaluation (Visit 3)

- 7-day Timeline follow-back procedure to assess self-reported medication adherence.
- Medication Adherence Scale

- Pill Count of 1 medication
- Valued Living Questionnaire
- Patient Health Questionnaire 9
- Positive and Negative Affect Scale- Short Form
- Perceived Stress Scale- Short Form.
- ENRICHD Social Support questionnaire
- Patient-Reported Outcomes Measurement Information System: Patient-Reported Outcomes Measurement Information System (PROMIS) Self-Efficacy for Managing Chronic Conditions- Managing Medications and Treatment- Short Form 4a
- Minnesota Living with Heart Failure Questionnaire (MLHFQ)
- EuroQual-5 Dimension (EQ-5D)
- Study and Treatment Acceptability. Participants will complete a self-report measure which gathers feedback about the study.

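### The SAP promises to include all randomized participants, but its end-of-treatment ANCOVAs have no missing-data method, and the unadjusted version is exposed to unequal dropout

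*SAP*

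**What the plan says.** - **Analysis set.** SAP, General Approach: "Intent-to-treat analyses will be used (i.e., all randomized participants will be included in analyses".
- **Method.** SAP, Analysis of Secondary Endpoints: "Analysis of covariance (ANCOVA) will be used to examine differences in self-reported adherence between groups at end-of-treatment". For electronic monitoring: "ANCOVA will be performed to examine differences in each outcome between groups at end-of-treatment". For the remaining scales: "Additional secondary analyses will use ANCOVA to examine differences in health-related quality of life, self-efficacy, perceived stress, affect and medication-related attitudes between groups". The section closes by saying that every secondary analysis is done both with and without covariates and the baseline score. It does not say which of the two carries the conclusion. Two-sided p below .05 is the criterion for both.
- **When outcomes are collected.** Protocol 4.1.3 places the follow-up questionnaires at Visit 3, including the "7-day Timeline follow-back procedure to assess self-reported medication adherence". Visit 2 (Protocol 4.1.2) has a pill count and, in one arm, the intervention session, but no questionnaires. The electronic cap is different: it is used to "monitor medications for approximately 8 weeks (from the baseline assessment through the end-of-treatment assessment".
- **Expected loss.** Protocol 1: "Participants will be randomized 1:1 basis to the Values-affirmation Intervention condition (n = 25) or Usual Care (n = 25". Protocol 6: "Feasibility of procedures will be defined as achieving a retention rate of 80" percent. The SAP's Baseline Descriptive Analyses compare completers with non-completers, on baseline characteristics only.
- **Missing data.** Neither document gives an imputation method, a likelihood-based repeated-measures model, a missing-data assumption or a sensitivity analysis.

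**The concern.** An ANCOVA of a Visit 3 score needs a Visit 3 score. With one post-baseline measurement and no rule for its absence, the model run as described uses only participants who attended the final visit, while the SAP says that everyone randomized is included. A reader of the results could take a completers comparison for an analysis of all 50.

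The label matters less than the choice between the two versions. Complete-case ANCOVA is unbiased when dropout depends only on baseline and arm, provided that baseline is in the model. The unadjusted version lacks that protection. If the two versions disagree, the plan does not say which to believe, although dropout alone could cause the disagreement. Unequal dropout is conceivable because only the intervention arm has an added session of about 60 minutes (Protocol 4.2).

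**Working it through.** The documents give no power calculation, SD or effect size, so there is no planned figure to reproduce.

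**1. How many could be left out.** Inputs: 50 randomized, 25 per arm (Protocol 1); 80% retention target (Protocol 6 and SAP).

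- With Visit 3 data at the target: 50 × 0.80 = 40. Without: 50 − 40 = 10.
- At 90% retention: 45 with, 5 without.
- Chance that nobody is missing, if losses are independent, is retention^50: 0.80^50 ≈ 0.00001; 0.90^50 ≈ 0.005; 0.95^50 ≈ 0.08.

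Some missing outcomes are therefore nearly certain at any retention close to the target. Ten is a ceiling at the target, for two reasons. Retention is counted from enrollment, while randomization follows the 30-day run-in (Protocol 4.1.1 and 4.2), so run-in losses are not in the randomized set. Also, under Protocol 6 a person who misses the intervention or the monitoring counts as a non-completer but may still have Visit 3 scores.

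**2. How far the unadjusted comparison can move.** With no treatment effect and loss that depends only on baseline:

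unadjusted bias = r × (difference between arms in mean baseline among completers, in SD)

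A completer imbalance of 0.27 SD gives 0.6 × 0.27 = 0.16 SD at r = 0.6, and 0.7 × 0.27 = 0.19 SD at r = 0.7. Both r and the dropout patterns are assumptions.

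The table comes from a null simulation with 25 per arm, r = 0.6 to 0.7 and 4,000 trials per setting. Selective losses are drawn with weight exp(−s × baseline in SD), so low scorers leave more often. The Monte Carlo standard error of a 5% rate is √(0.05 × 0.95 / 4000) ≈ 0.3 percentage points.

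| Lost (intervention v control) | Where loss depends on baseline | Unadjusted bias, SD | Unadjusted false positives |
|---|---|---|---|
| 7 v 3 | intervention only, s = 0.5 | about 0.10 | 6–7% |
| 7 v 3 | intervention only, s = 1 | 0.16–0.19 | about 8–10% |
| 7 v 3 | intervention only, s = 2 | 0.22–0.26 | above 10% |
| 7 v 3 | both arms, s = 1 | about 0.10 | 6–7% |
| 4 v 2 | both arms, s = 1 | 0.04–0.05 | 5–6% |
| 5 v 5 | both arms, s = 1 | about 0 | 5–6% |

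In every row the baseline-adjusted complete-case ANCOVA had bias within about 0.01 SD and rejected about 5% of the time.

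**3. Cross-check without a dropout model.** If non-completers would have scored g SD below completers in both arms, the completers difference departs from the all-randomized difference by (missing share in one arm − missing share in the other) × g. With 30% v 10% missing: 0.20 × 0.5 = 0.10 SD, or 0.20 × 1.0 = 0.20 SD. With 20% v 20% it is 0. This agrees in size with the table.

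**The case against.** The strongest reply is that the SAP has an omission and no outright contradiction. It states no complete-case rule, and ANCOVA after multiple imputation would satisfy the intent-to-treat sentence. That stands: a reader might infer that ANCOVA cannot deliver the stated property, and the documents do not support this. What is missing is the method that would deliver it.

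Other parts of the reply also stand:

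- A reader might infer that the two versions have equal standing. The SAP ranks neither, and since ANCOVA is the named method, the unadjusted run may be meant as supportive. The gap is the absence of a ranking.
- Arm-differential, baseline-dependent loss is assumed. Against it, home visits are offered (Protocol 1 and 4.1.2) and $60 of the $90 is paid after Visit 3 (Protocol 5). Protocol 4.2 has assignment disclosed on arrival at Visit 2, where the session takes place, although Protocol 4.1.2 has it disclosed by telephone beforehand.
- A reader might infer that a repeated-measures model is needed as the lead analysis. With a single follow-up, a participant without Visit 3 adds only a baseline value. It keeps everyone nominally but recovers no lost outcome, and no gain over adjusted ANCOVA has been shown.
- Electronic monitoring runs continuously, so a missed Visit 3 need not remove that outcome. The SAP has no rule for partial monitoring, but that and the endpoint's definition are separate questions.

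None of this supplies a missing-data method or says which version leads.

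**Conclusion.** The concern holds in limited form. As written, the plan does not deliver its own definition of intent-to-treat for the secondary questionnaire endpoints: participants without Visit 3 have no route into the ANCOVA. At the 80% target at most 10 of 50 are affected.

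The practical exposure lies in the unranked, unadjusted analysis. Under assumed baseline-dependent loss that differs by arm, with r of 0.6 to 0.7, its bias is roughly 0.10 to 0.2 SD with about 6 to 10% false positives. It is worse under steeper selection, smaller when the losses are fewer and less unequal, and about 0 when they are balanced. The baseline-adjusted version is sound in all these settings.

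A reader might go further and infer that the trial's results will be biased. The documents do not support that, because they contain no evidence on the pattern of dropout. The affected comparisons are secondary, in a pilot whose primary endpoints are descriptive. The change is worth making, but the trial's main purpose does not depend on it.

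**What to change.** 1. For each secondary endpoint with a baseline score, name the baseline-adjusted ANCOVA as the single inferential analysis. Show the unadjusted result descriptively, without a significance test.
2. Then choose one of two options:
   - Replace the intent-to-treat sentence with: *analysed as randomized, participants with end-of-treatment data*. Report the number analysed and the number missing in each arm.
   - Keep the sentence and name a method that includes everyone: multiple imputation, or a repeated-measures model with baseline and Visit 3 both as outcomes.

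The first option costs only SAP wording; the second adds one standard procedure. No extra data collection is needed. The small downside is that either option still assumes that dropout is explained by observed data, and neither recovers the outcomes that were lost.

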- Following completion of the Baseline monitoring period, study staff will contact the participant and inform the participant of their randomization assignment via telephone, and schedule Visit 2. Visit 2 will be conducted either at the participant's home or the study office, as determined by participant preference. Individuals assigned to the Intervention condition will also complete the intervention at this session (see details in Section 6). For participants in both conditions, we will again conduct a pill count of ONE medication per patient using the criteria adopted by Wu et al. described above.

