4.2 Interventions, Administration, and Duration

Following completion of the baseline adherence monitoring period, participants will be randomly assigned to one of two conditions. Participants will be scheduled for Visit 2 at the end of the baseline adherence monitoring period. Participants will be randomized and notified of group assignment upon arrival to Visit 2.

Group A (Usual Care): Participants assigned to Group A will receive the standard care that they would receive as part of cardiac rehabilitation.

Group B (Values affirmation intervention condition): Participants assigned to Group B will receive standard care in addition to the Values affirmation intervention condition. Participants will complete a one intervention session with the study interventionist (about 60 minutes). The session will include:

1. Participation in a values-affirmation exercise (i.e., Values card sort activity).
2. Working with the interventionist to devise a way to tangibly connect that value with medication-taking (i.e., placing a label with a word or picture of the value on a pill bottle or display next to the pill bottle). Values labels will be based on images presented on the values card sort cards or personalized pictures taken with a Lifespan-issued tablet and printed on site with a portable photo printer. Once the picture is printed it will be deleted from the tablet.
3. Provision and review of a patient education workbook that recommendations for skills training activities to improve regimen management.

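### The SAP drops intervention completion from the primary retention endpoint, so the same data can pass the 80% rule under the SAP and fail it under the Protocol

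*SAP*

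**What the plan says.** The SAP, under Analysis of Primary Endpoints, item 2, reads: "Retention will be calculated as the percentage of individuals who were enrolled and completed both the baseline assessment, monitoring periods, and end-of-treatment assessment". The intervention is not mentioned.

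Protocol section 6, item 2, counts those who "completed both the baseline assessment, intervention (when applicable), monitoring period, and end-of-treatment assessment". Protocol section 1, Study Duration, agrees: "Study completion is defined as completion of the baseline and end-of-treatment assessments, intervention content, and medication monitoring period".

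Both documents then apply the same rule. The Protocol's wording is "Feasibility of procedures will be defined as achieving a retention rate of 80" per cent, and the SAP repeats it. The Protocol labels the item study feasibility and the SAP labels it retention, but in both it feeds the one 80% criterion. Nothing later in the SAP restores session completion, explains its absence or says which document takes precedence.

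**The concern.** This is a primary endpoint with a pass/fail threshold in a Stage 1B trial whose stated purpose is to assess feasibility and acceptability. An intervention-arm participant who misses the one session but completes monitoring and the final evaluation is a success under the SAP and a failure under the Protocol. The feasibility verdict can then depend on which document the analyst opens, possibly with the data already in view. As written, SAP item 2 would return the same figure if no session had been delivered at all.

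The difference also reaches the SAP's baseline comparison of completers with non-completers. The SAP does not define those groups, so their membership depends on the same choice.

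**Working it through.** **Inputs from the documents.** Planned sample 50, allocated 25 and 25 (Protocol section 1). Threshold 80% (Protocol section 6 and SAP item 2), read as at least 80%. One session of about 60 minutes, intervention arm only (Protocol 4.2), held at Visit 2 (Protocol 4.1.2). Final evaluation at Visit 3 (Protocol 4.1.3). The primary endpoints are analysed descriptively and the documents derive no figure for this endpoint, so there is no plan calculation to reproduce.

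**Assumptions.** The enrolled denominator is 50. Randomization follows a 30-day run-in, so enrolment could exceed the number randomized; that would change the counts but not the conflict. The SAP's plural monitoring periods and the Protocol's singular monitoring period are taken to mean the same monitoring of about 8 weeks.

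**Step 1, threshold as a count.** 0.80 × 50 = 40.

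**Step 2, the two rates.** Let R be the number completing the baseline assessment, monitoring and the end-of-treatment assessment, and m the number of intervention participants among them who did not complete the session.

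- SAP rate = R/50
- Protocol rate = (R − m)/50

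Since m ≥ 0, the SAP rate is never the lower of the two. They are equal only when m = 0.

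**Step 3, when the verdicts differ.** R ≥ 40 and R − m ≤ 39, that is m ≥ R − 39.

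| R | SAP rate | Smallest m that reverses | Protocol rate |
|---|---|---|---|
| 40 | 80% | 1 | 39/50 = 78% |
| 41 | 82% | 2 | 39/50 = 78% |
| 42 | 84% | 3 | 39/50 = 78% |
| 45 | 90% | 6 | 39/50 = 78% |
| 50 | 100% | 11 | 39/50 = 78% |

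**Step 4, chance of opposite verdicts at a given R.** The documents give no session-completion rate, so the missed-session probability q is an assumption. Take m ~ Binomial(n, q), with n = R/2 rounded down, and compute P(m ≥ R − 39).

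| R | n | q = 5% | q = 10% | q = 20% |
|---|---|---|---|---|
| 40 | 20 | 0.64 | 0.88 | 0.99 |
| 42 | 21 | 0.085 | 0.35 | 0.82 |
| 45 | 22 | 0.0006 | 0.018 | 0.27 |

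**Step 5, averaged over R.** Step 4 fixes R, and R = 40 is the most sensitive case. Let the number retained in each arm be Binomial(25, p), with p also assumed, and sum the chance of opposite verdicts over all outcomes with R ≥ 40.

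| True retention p | q = 5% | q = 10% | q = 20% |
|---|---|---|---|
| 80% | 0.14 | 0.27 | 0.45 |
| 85% | 0.11 | 0.24 | 0.54 |
| 90% | 0.03 | 0.09 | 0.34 |
| 95% | 0.001 | 0.007 | 0.09 |

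**Step 6, can a participant be retained without the session?** Protocol 4.1.2 has staff "inform the participant of their randomization assignment via telephone, and schedule Visit 2", so assignment can be known before the visit at which the session is given, and the session can then be missed. Protocol 4.2 says instead: "Participants will be randomized and notified of group assignment upon arrival to Visit 2". On that reading, mainly an on-site refusal or an unfinished session would separate the two definitions. The two sections conflict, so neither reading can be relied on to rule the pattern out.

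**The case against.** The wording difference is not in dispute. The case against concerns its size and the remedy.

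- **The largest probabilities are conditional.** The 64% to 99% figures hold only if exactly 40 are retained. This stands, and the averaged figures in step 5 are the fairer summary. The 20% column also requires one in five retained intervention participants to miss the only session, which nothing in the documents supports or excludes.
- **The route is narrow if assignment happens on arrival at Visit 2.** Someone who skips that visit would then never be assigned, and the intervention arguably would not apply to them. This stands in part: it would lower the chances above, but Protocol 4.1.2 says otherwise. The payment schedule in Protocol section 5 (after Visits 1 and 3 only) is at most a weak hint that Visit 2 could be skipped, and the point does not need it.
- **Assessment-only retention is a legitimate meaning of retention.** True, but the SAP does not present it as a deliberate change, and the Protocol states the wider definition twice.
- **The composite is a weak check on delivery.** If all 50 are otherwise retained, 10 of 25 intervention participants (40%) could miss the session and the composite would still be 40/50 = 80%. This stands, and it is why session completion should also be reported separately.
- **The analysis is descriptive.** At 40/50 the exact 95% interval is about 66% to 90%, so a shift of one or two participants (2 to 4 percentage points) is small against sampling error. That is correct for estimation, but the plan declares success or failure on the point value at 80%.

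**Conclusion.** The concern holds. One primary pass/fail criterion has two definitions, the SAP's is the more lenient, and nothing says which governs. With 50 enrolled, between 1 missed session (40 retained) and 11 (50 retained) reverse the verdict.

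The practical size is unknown and depends on assumed rates. The mismatch matters when retention is near 80%, and matters little when it is about 90% or higher with few missed sessions. The one-way direction assumes that the two monitoring terms mean the same thing. It should be fixed because it concerns the definition of a primary endpoint; that case does not depend on any one of the probabilities.

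**What to change.** In SAP item 2, restore completion of the intervention for those to whom it applies, so that the item matches Protocol section 6, item 2. Use the same monitoring term in both documents and state that the 80% rule applies to this composite. Report two supporting figures: assessment-and-monitoring retention among all enrolled, and session completion among those assigned to the intervention. Define completers in the baseline comparison by the same rule. Protocol 4.1.2 and 4.2 should also be reconciled on when assignment is made known, since that determines to whom the intervention applies.

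The retention fix changes SAP wording only and needs no new data. The reported rate may be slightly less favourable, and no information is lost. The change should be made before the data are analysed.

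### SAP secondary endpoint 2 scores electronic adherence as a raw count of days with no denominator, although the number of days monitored is not fixed.

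*SAP*

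**What the plan says.** SAP, Analysis of Secondary Endpoints, item 2: "Electronically-monitored medication adherence measured the number of days" on which at least 80% of prescribed doses were taken. Groups are compared by ANCOVA at end-of-treatment. No denominator is given, and no first or last counting day. The SAP adds that secondary analyses are run with and without covariates and the baseline score on the same endpoint. It does not name the covariates or say that days monitored is one of them. Under General Approach, "all randomized participants will be included in analyses".

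The protocol supplies the timing:

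- Section 1: "Individual participants will complete the protocol within 8-10 weeks from the time of the baseline visit until the end-of-treatment assessment".
- Section 4.1.1: participants use the cap to "monitor medications for approximately 8 weeks (from the baseline assessment through the end-of-treatment assessment". Cap use starts the day after the baseline visit.
- Section 4.1.1, on the run-in: "the intervention will start 30 days later; this 30-day period will be considered our baseline".
- Section 4.1.2, once the run-in is complete: "study staff will contact the participant and inform the participant of their randomization assignment via telephone, and schedule Visit 2".
- Section 4.2: "Participants will be scheduled for Visit 2 at the end of the baseline adherence monitoring period".

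No day window is given for Visit 2. Protocol Section 6 lists only primary endpoints, so it does not define this measure.

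**The concern.** A count of days measures adherence only if everyone is observed for the same number of days. Here the interval between the baseline visit and the end-of-treatment assessment may differ by two weeks between participants. The count therefore mixes how well a person took the medication with how long the cap was in use.

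Two things follow if the wording is applied literally. Participants with the same adherence receive different scores. And because all randomized participants are to be analysed, someone whose monitoring stops early receives a low score that may say nothing about adherence. At stake is the precision and readability of a secondary comparison that the SAP plans to test at p < .05 with about 25 participants per arm.

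**Working it through.** **Reproduction.** The documents give no effect size, SD or power for this endpoint, so there is no stated figure to reproduce.

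**Window length, from the documents.** Post-run-in days = total days − 30.

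- 8 weeks: 8 × 7 − 30 = 26 days.
- 10 weeks: 10 × 7 − 30 = 40 days.
- If the day of the baseline visit is excluded because cap use starts the next day, the range is 25 to 39.

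This is the range from the end of the run-in. If counting starts at Visit 2 and Visit 2 falls later, the window is shorter by the delay. The documents do not bound that delay.

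**Score at a given adherence.** Expected count = adherence rate × days monitored.

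- 80% of days: 0.80 × 26 = 20.8; 0.80 × 40 = 32.0. The gap is 11.2 days with no difference in adherence.
- Reversal at the two limits: 0.60 × 40 = 24.0 exceeds 0.90 × 26 = 23.4.
- Early stop halfway through a 26-day window: 0.80 × 13 = 10.4, against 20.8 for the same adherence observed in full.

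**Cost in power (illustrative).** These inputs are assumed and are not in the documents: mean adherent-day rates 0.80 v 0.90, and between-person SD 0.10, 0.15, 0.20 or 0.25. The arm size of 25 and the two-sided 0.05 level are the plan's. Person rates were beta-distributed with binomial day-to-day variation. Window lengths were uniform with the same distribution in both arms, and everyone completed monitoring. The test was a two-sample t-test, with 100,000 replicates.

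| Windows (days) | Measure | SD 0.10 | SD 0.15 | SD 0.20 | SD 0.25 |
|---|---|---|---|---|---|
| 26-30 | count | 0.777 | 0.553 | 0.403 | 0.300 |
| 26-30 | proportion | 0.822 | 0.582 | 0.419 | 0.309 |
| 26-40 | count | 0.572 | 0.432 | 0.331 | 0.260 |
| 26-40 | proportion | 0.835 | 0.593 | 0.418 | 0.315 |
| 26-40 | count, common first 26 days | 0.815 | 0.581 | 0.414 | 0.312 |

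Loss from using the count (proportion minus count, in points):

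- 26-30 days: 4.5, 2.9, 1.6, 0.9.
- 26-40 days: 26.3, 16.1, 8.7, 5.5.

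With no true effect, both measures reject in 4.8-5.2% of replicates (20,000 replicates).

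**Check under the planned ANCOVA.** Adjusting for the run-in count, with an assumed correlation of 0.6 between a person's underlying run-in and later rates (4,000 replicates), shows the same pattern. At 26-40 days the count gives 0.596/0.491/0.371/0.293 and the proportion 0.880/0.679/0.496/0.368. At 26-30 days the figures are 0.824/0.655/0.479/0.353 and 0.870/0.690/0.497/0.365.

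**The case against.** The strongest reply is that the protocol already implies the window and that little is lost in practice. Section 4.1.1 fixes the start of cap use, a 30-day baseline and monitoring through the end-of-treatment assessment, so the natural window runs from the end of the run-in to Visit 3. The SAP sentence is incomplete, and a percentage may have been meant. Monitoring is described as about 8 weeks, and 10 weeks is an outer limit. If windows cluster near 8 weeks (assumed triangular, mode 26, maximum 40), count v proportion is 64 v 83%, 47 v 59%, 35 v 42% and 27 v 31% across the same four SDs. That is smaller than the widest case. The reversal example needs two participants at opposite limits. The endpoint is secondary, in a pilot.

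Most of this stands and sets the size of the point. It does not remove it: an implied window still has a variable length, and neither document says that the count is divided by that length.

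A reader might infer three stronger things that the documents do not support:

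- *That the baseline adjustment is invalid because the run-in score is out of 30 days and the later score is not.* No planned analysis uses a change score in adherence. ANCOVA does not need the covariate in the outcome's units, and a count over a fixed 30 days is simply the run-in proportion times 30.
- *That the arm comparison is biased.* Bias would need window length, or early stopping, to differ by arm. Both arms have a Visit 2, and nothing in the documents says that windows will differ.
- *That the conflict over how assignment is notified bears on this endpoint.* Section 4.1.2 has a telephone call, whereas Section 4.2 says "Participants will be randomized and notified of group assignment upon arrival to Visit 2". That is a separate inconsistency. Only when Visit 2 takes place matters for the counting window.

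**Conclusion.** The point holds as a cheap improvement. The SAP states a count, the protocol lets the observation time vary, and the count therefore scores equal adherence unequally. With windows balanced by arm, the type I error rate stays near 5% and the cost is precision alone. That cost is slight if monitoring stays near 8 weeks, and material only if windows spread widely towards 10 weeks and participants are fairly alike in adherence. The power figures rest on assumed rates, SDs and window distributions, and on everyone completing monitoring. They show the order of size and are not forecasts. No power figure can be given for early stopping, because the plan states no scoring rule for it. The primary feasibility and acceptability conclusions do not depend on this endpoint.

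**What to change.** Amend SAP item 2 in one of two ways:

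1. Define the endpoint as adherent days divided by days monitored. The window runs from a stated start (end of the run-in, or Visit 2) to the end-of-treatment assessment, or to the documented date the cap was stopped if that is earlier.
2. Count adherent days over one common fixed window for every participant.

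Express the run-in value in the same form, for readability, and report days monitored by arm so that balance can be seen. Reconcile the monitoring duration in protocol Sections 1 and 4.1.1, and the timing of Visit 2 in Sections 4.1.1, 4.1.2 and 4.2.

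The cost is SAP wording and a recorded stop or return date for each cap, with no extra visits or measures. There are downsides. Proportions from short windows are noisier, and they treat unobserved days as like observed ones. A participant with no monitored days has no proportion, so the SAP should say how such a participant is handled among all randomized. A common window discards later days and still needs a rule for anyone who does not reach its end.
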